#### 4. ANALYSIS SETS

For purposes of analysis, the following populations are defined:

Analysis Set	Description
Enrolled Set	
The Enrolled Analysis Set will include all participants who provide informed consent for this study.
 
This analysis set will be used to summarize participant disposition, protocol deviations (as classified in Clinical Trial Management Software), and inclusion/exclusion from the Safety Set, including reasons for exclusion from it.

Safety Set	
All participants who take/receive at least 1 dose of study intervention (XYWAV).
 
This analysis set will be used for reporting analyses of safety endpoints.

Completer Set	
All participants who complete the EOT Visit after 6 weeks of study intervention with a 24-hour BP recording at this visit that meets the minimal data standards.
 
This analysis set will be used for primary analyses of effectiveness endpoints.

Effectiveness Set	
All participants who complete at least one post-baseline study effectiveness assessment (including early discontinuation).
 
This analysis set will be used for reporting sensitivity analyses of effectiveness endpoints.

#### 5. GENERAL ASPECTS FOR STATISTICAL ANALYSIS

The statistical principles applied in the design and planned analyses of this study are consistent with International Conference on Harmonization (ICH) E9 guidelines (ICH 1998).

##### 5.1. General Methods

All study data will be summarized using descriptive statistics. Categorical variables (e.g., race, ethnicity) will be reported as frequency and percent. Continuous variables will be reported as number of participants, mean, SD, median, minimum, and maximum (eg, age, weight). All summaries, statistical analyses, and individual participant data listings will be performed with SAS version 9.4 or later (SAS Institute, Inc.; Cary, NC). Tables, Listings, and Figures (TLFs) specifications are in another document which is incorporated by reference.

## 5.2. Baseline and Study Day Definitions

### 5.2.1. Baseline

In this study, the screening period includes all measurements taken after informed consent is obtained until Day 1. Baseline refers to the most recent observation prior to Day 1.

### 5.2.2. Study Day

Day 1 is defined as the first day of interventional XYWAV use. Study day will be calculated as:

$$\text{Study Day} = (\text{date of assessment} - \text{date of first dose of XYWAV}) + 1$$

The intervention period extends from Day 1 until end of XYWAV.

### 5.2.3. Visit Windows

Listings will include all recorded assessments.

Unless otherwise specified, all data will be summarized using the CRF visit at which the data was collected. If a participant early discontinues, an ED Visit should be conducted as soon as possible after last study dose of XYWAV (or preferably while still on treatment).

Unscheduled visits in general will be excluded from analyses where the corresponding scheduled visit is present. Unscheduled visits will only be mapped to a scheduled visit if the scheduled visit record is missing. If more than one unscheduled visit can be mapped to a visit window, the one with the assessment date closest to the target study day will be selected. If two visits are equally close to the target day (but on different sides), the later visit will be mapped.

If multiple assessments or measurements are recorded within a single visit window (including unscheduled, repeated, and retest assessments or measurements), the following rules will be applied to determine which assessment or measurement will be used for the summaries for that analysis visit.

- If there are two or more results within the same visit window, then the latest one will be used in the analysis.
- If two observations are equidistant from the scheduled period day, then the observation with the latest collection date will be used in the analysis.
- If two observations are collected on the same day and this day is the closest to the scheduled period day, then the observation with the earliest collection time will be included in the analysis.

If a visit window does not contain any observations, then the data will remain missing.

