#### **8.3.2. Vital Signs**

##### **8.3.2.1. Blood Pressure and Other Vitals**

- BP and pulse measurements should be obtained at the investigational site using the sponsor-provided device (site-based participants) or at the participant's home location with study personnel using the sponsor-provided device (decentralized participants). The same device should be used for each measurement to ensure consistency for a given participant.
- BP and pulse measurements should be preceded by at least 5 minutes of quiet rest (ie, no talking) and obtained while the participant is seated in a quiet setting without distractions (eg, television, cell phones).
- BP and pulse measurements will be obtained using a sponsor-provided OBPM device. Once initiated, this device will start a 5-minute countdown (ie, a rest period), followed by 3 consecutive BP and pulse rate measurements with 1-minute intervals between each measurement. The device will then automatically calculate and record an average for the 3 BP and 3 pulse rate readings (calculated and recorded separately for SBP and DBP).

- At the Screening Visit, BP and pulse measurements should be obtained before blood collection for laboratory tests. BP and pulse may be repeated up to 2 additional times if the investigator considers that the average recorded by the device was unduly influenced by transitory factors (eg, excessive movement or loud noises during measurement). All screening measurements should be reviewed and filed in the source documents. The investigator will select only 1 recording average for purposes of study eligibility.

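### SAP 5.2.1 and 5.2.3 give conflicting rules for which same-day Screening Visit recording is the seated-SBP baseline, and one of them picks the recording that prompted the repeat

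*SAP*

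**What the plan says.** **Repeats at screening.** Protocol 8.3.2.1: "BP and pulse may be repeated up to 2 additional times if the investigator considers that the average recorded by the device was unduly influenced", with movement and noise during measurement as the examples. Each recording is a device average of three readings, so up to three averages can exist. On handling them the protocol says "All screening measurements should be reviewed and filed in the source documents" and "The investigator will select only 1 recording average for purposes of study eligibility".

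**Baseline.** SAP 5.2.1: "Baseline refers to the most recent observation prior to Day 1". Protocol 9.3.1.1 gives the same definition.

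**Several results in one visit window.** The rules in SAP 5.2.3 cover multiple results, "including unscheduled, repeated, and retest assessments or measurements". The first bullet reads: "If there are two or more results within the same visit window, then the latest one will be used in the analysis". The third bullet covers two observations on the same day, where that day is closest to the scheduled day: "then the observation with the earliest collection time will be included in the analysis".

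**Use of the endpoint.** Change in seated resting SBP is third in the fixed testing sequence (Protocol 9.1.1, SAP 5.4). Nighttime SBP, fourth, is tested only if the third succeeds.

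**The concern.** The Screening Visit recordings are the only scheduled seated measurements before Day 1, because neither Schedule of Activities table has vital signs at Visit 2. Whenever a repeat was taken, the choice among these same-day recordings therefore fixes the baseline, and the SAP gives incompatible instructions for that choice. Two programmers following it could derive different baselines.

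The earliest-time instruction is the troublesome one. A repeat is permitted only "if the investigator considers that the average recorded by the device was unduly influenced by transitory factors", so when a repeat exists, the first recording is one whose average the investigator had doubted. The repeat provision applies only to the Screening Visit. A distorted first recording would therefore enter the baseline side of the change score, with no matching process at end of treatment (EOT). In a single-arm study no control group absorbs the error. A first recording that is too high looks like a fall after the switch, and one that is too low hides a fall.

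**Working it through.** The plan states no figure on this point, so there is none to reproduce. The check applies the rules to an example and then asks how a baseline error reaches the estimate.

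**1. The rules applied to one participant.** Assumed same-day averages, in order: 162, 150 and 148 mm Hg. The investigator selects the second for eligibility.

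- SAP 5.2.3, third bullet (earliest time): 162. This is the doubted value. It lies above the 155 mm Hg upper limit given in the Amendment 04 rationale.
- SAP 5.2.1, Protocol 9.3.1.1 and SAP 5.2.3, first bullet (most recent or latest): 148. This is not the selected value either.
- Protocol 8.3.2.1 (investigator's selection): 150, but for eligibility only.

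Three recordings thus have a claim, and no text ranks them. Within 5.2.3 itself, the first bullet already decides every case of two or more results in a window. The third bullet can matter only as a same-day exception to it, or else it is left over from a closest-to-target-day rule. The SAP does not say which.

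**2. How a baseline shift reaches the estimate.** Protocol 9.3.2 and SAP 7.1.1 fit change = a + b × (baseline − mean baseline), and SAP 7.2.1 applies this to the secondary endpoints. The centred covariate sums to zero, so the estimate of a (the LS mean) equals mean change = mean EOT − mean baseline. If a share f of participants has a baseline that is too high by d on average, mean baseline rises by f × d and the LS mean change falls by f × d. The covariate adjustment does not remove it.

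**3. Size by assumption.** The documents give neither f nor d. The shift f × d in mm Hg is:

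| f | d = 3 | d = 5 | d = 10 |
|---|---|---|---|
| 10% | 0.3 | 0.5 | 1.0 |
| 20% | 0.6 | 1.0 | 2.0 |
| 30% | 0.9 | 1.5 | 3.0 |

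**4. Illustration with the protocol's own repeat trigger.** Assumptions: true seated SBP has mean 135, 142 or 148 and SD 11; the within-visit SD of a device average is 5 or 7; 20% of first averages carry a +8 mm Hg artefact; each of these is repeated once and the second is selected; and participants enter if the selected average is 130 to 155. Without the range condition the shift is 0.20 × 8 = 1.6. With it, simulation gives 1.3 to 1.8 mm Hg, lowest at a true mean of 135 and highest at 148. In 4% to 9% of those enrolled, the first recording lies outside 130 to 155.

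For scale, the planning effect is 3.0 to 3.5 mm Hg (Protocol 9.5). That figure is for 24-hour ambulatory SBP; none is given for seated SBP.

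**The case against.** The strongest reply is that the SAP has an explicit baseline definition, which means the last repeat, and that 5.2.3 only picks values for visit summaries. The third bullet also depends on a scheduled day, while SAP Table 3 gives Visit 1 as the range -21 to -1. This is a fair reading and perhaps the more natural one. It does not settle the matter. SAP Table 3 labels Visit 1 as screening and baseline, the 5.2.3 rules expressly reach repeats, and if all recordings fall on one day, that day is trivially the closest. Even on this reading, the last recording need not be the one selected.

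Second, the protocol requires every recording to be filed in source documents but does not say that each is entered in the eCRF. If only the selected average is entered, the conflict never arises. That stands, and the conclusion is conditional on it. Inclusion criteria 6 and 7, which govern these readings, are not visible in the public text.

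Third, the first recording is doubted, not void. The investigator may review all of them and still select it. That also stands.

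Finally, a reader might model repeats as triggered by an average outside the eligibility range. That would give larger shifts in both directions and more out-of-range baselines. The protocol's stated trigger is transitory influence, so the documents do not support those figures. They would also mix in the selection effect of requiring the chosen value to be in range.

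**Conclusion.** The contradiction is real and should be resolved before the seated-SBP endpoint is derived. Earliest competes with latest or most recent, no precedence is stated, and baseline is not linked to the investigator-selected average.

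A reader might infer that the SAP definitely makes the first recording the baseline, or that a rejected value will be analysed. The documents support neither. They support only that a doubted value can become the baseline if all repeats reach the analysis data and the same-day rule is the one applied.

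The reach is limited to hypothesis 3 and, through gating, hypothesis 4. The primary and daytime endpoints come from ambulatory monitoring, are tested earlier, and are unaffected. The size cannot be estimated from the documents. The 1.3 to 1.8 mm Hg shift rests wholly on the assumed 20% frequency, +8 mm Hg artefact and distributions in the working, and any shift would pass in full into the LS mean change.

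**What to change.** In SAP 5.2.1 and 5.2.3:

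- State that the earliest-time same-day rule does not apply to baseline, and that 5.2.1 takes precedence over 5.2.3 for baseline.
- Name one recording as the seated-SBP baseline: either the single Screening Visit average selected by the investigator, flagged in the dataset, or the most recent recording under 5.2.1.
- Report a sensitivity analysis using the other recording.

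The cost is a sentence or two in the SAP and a dataset flag. Sample size and alpha levels do not change. The selected recording would have to be flagged for participants already screened as well. If the selected average is used, an open-label choice tied to eligibility enters the baseline of a confirmatory endpoint, which is why the sensitivity analysis is needed. The most-recent option avoids using that choice directly, but the baseline may then differ from the value that qualified the participant.

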**Table 3: Visit Windows for Assessments or Measurements**

Study Period	Study Visit	Target Study Day
Screening, Baseline	Visit 1	-21 to -1
Intervention	Visit 2	1
Intervention	Visit 3	7 ± 3

Intervention	Visit 4	14 ± 3
Intervention	Visit 5	28 ± 3
Intervention	Visit 6	35 ± 3
Intervention	Visit 7	42 ± 3
Follow-up	Visit 8	56 ± 3

#### 5.2.4. Missing and Partial Data

Participants who drop out will not be replaced. All reported data will be included in the summaries without imputation of any missing data. Analysis datasets will include derived records for last observed value to facilitate supplemental analyses in which participants who discontinue the study are included.

Missing or partially missing start and stop dates for adverse events and concomitant medications will be imputed where necessary according to rules defined in Appendix 1 and Appendix 2. Listings will include verbatim dates as entered.

In Demographics summary tables, the age entered by the sites will be used. If it is missing, then it will be derived from date of birth and informed consent date if available. For countries where regulations allow only the year of birth to be entered for birth date, July 1st of that year will be used for the calculation of age.

ABPM-based endpoints are subject to ABPM data adequacy criteria, defined in a separate specification document which is incorporated by reference. Device-provided summaries marked as "Valid" or "Valid Within Acceptable Limits" shall be eligible for analysis. If satisfactory data are not acquired on initial attempt, repeated 24-hour ambulatory measurements are permitted per protocol. If valid sleep diary entries covering the ABPM period are not available, the weekly mean sleep/wake time described in Section 8.1.3 may be used for creating the daytime/nighttime windows (Section 7.2.2).

### 5.3. Hypothesis Testing

The primary statistical hypothesis for this study is that there will be a clinically relevant decrease in 24-hour average SBP, compared to baseline, after switching from high-sodium oxybate to XYWAV for 6 weeks. The null and alternative hypotheses for the primary endpoint are:

$$H_0: \Delta_{SBP} = 0; H_1: \Delta_{SBP} < 0$$

Similarly defined hypotheses will be tested for the secondary endpoints of change in daytime and nighttime average SBP (both assessed using 24-hour ambulatory BP monitors) and change in seated resting SBP (assessed using the measurements performed by the site personnel).

## 5.4. Level of Significance & Multiplicity Adjustment

To control family-wise error rate inflation due to multiple endpoints and the interim analysis (Section 3.5), a fixed hierarchical testing sequence will be employed. Testing begins with the first endpoint at the specified alpha level and continues through the sequence until an endpoint is not statistically significant. Remaining analyses will be considered exploratory and associated p-values will be considered nominal.

The Type I error rate for study endpoints will be set at a one-sided level of 0.025. To account for the possibility of ending the study at the interim analysis, statistical significance for the primary endpoint (#1) will be assessed using O'Brien-Fleming one-sided alpha levels of 0.00998 for the interim analysis and 0.02194 for the final analysis. Statistical significance for each of the secondary endpoints (#2 to #4) will be assessed using the Pocock one-sided alpha level of 0.0168 at either the interim or final analysis.

Statistical hypotheses to be tested (in sequential order):

1. Change in the 24-hour average SBP (mm Hg) following 6 weeks of XYWAV treatment after switching from high-sodium oxybate in participants with narcolepsy
2. Change in the daytime average SBP (mm Hg) following 6 weeks of XYWAV treatment after switching from high-sodium oxybate in participants with narcolepsy
3. Change in the seated resting average SBP (mm Hg) following 6 weeks of XYWAV treatment after switching from high-sodium oxybate in participants with narcolepsy
4. Change in the nighttime average SBP (mm Hg) following 6 weeks of XYWAV treatment after switching from high-sodium oxybate in participants with narcolepsy

Analyses not part of this hierarchy will be considered exploratory, and no multiplicity adjustment will be performed. P-values reported in standard table outputs will be considered nominal.

## 5.5. Subgroups and Subgroup Analyses

Summary output tables will report results overall and within narcolepsy subtype. Additional subgroup analyses may be conducted on the primary and key secondary efficacy endpoints for the following:

- Baseline use of antihypertensive medication
- Source of enrollment (traditional site-based vs. decentralized)
- Geographic region

---

Multiple Endpoints in Clinical Trials. 2017; Available from:  
<https://www.fda.gov/files/drugs/published/Multiple-Endpoints-in-Clinical-Trials-Guidance-for-Industry.pdf>

## **5.6. Changes to Planned Analyses**

N/A

## **6. STUDY POPULATION SUMMARIES**

### **6.1. Enrollment**

The total number and percentage of participants for each Analysis Set defined in Section 4 will be summarized. The number of participants who enrolled by country and study site/investigator will be summarized.

### **6.2. Subject Disposition**

Disposition of all participants who provide informed consent will be accounted in this study. For each period, the number and percentages of participants who entered, received at least one dose, completed, are still ongoing (for interim analyses), and early discontinuation will be presented using the enrolled analysis set. Reasons for screen failure and early discontinuation will be presented in descending order of frequency; participants with missing reasons will be reported as the last row.

### **6.3. Demographic and Baseline Characteristics**

Demographic variables and other baseline characteristics will be summarized using descriptive statistics separately for Safety Set and Completer Set.

### **6.4. Medical/Surgical History**

Medical history will be obtained by the investigator or a medically qualified designee (consistent with local regulations). All active conditions and any condition diagnosed within the participant's lifetime that the investigator deems clinically significant should be recorded.

Surgical and medical history will be coded using the Medical Dictionary for Regulatory Activities (MedDRA) dictionary, version 26.0 or later, and summarized by system organ class (SOC) and preferred term (PT) using the Safety Set.

If a participant reports a medical condition/disease, surgery, or medication more than once within a SOC or PT, the entry will be reported only once for that SOC or PT.

### **6.5. Prior and Concomitant Medications**

The investigator or medically qualified designee should review the participant's prior medication use. All medication currently taken by the participant should be recorded.

- Prior medications are defined as any medications which started prior to the first dose of XYWAV.
- Concomitant medications will be defined as any medications with a stop date on or after the first conversion from Xyrem to XYWAV, during the study, or any medication that is

ongoing. A medication with completely missing use dates or partially missing use dates without evidence that the medication was stopped prior to the first dose of study drug will be considered a concomitant medication.

Prior and concomitant medications will be coded with the Anatomical Therapeutic Class (ATC) level 4 and preferred drug name using the World Health Organization (WHO) drug dictionary, version Mar 2022 or later. Unique medications will be summarized by ATC level 4 and preferred drug name using the Safety Set. A listing will also be presented.

Hypertension medications (based on ATC Level 3) will be summarized:

- C02 – Antihypertensives
- C03 – Diuretics
- C07 – Beta blocking agents
- C08 – Calcium channel blockers
- C09 – Agents acting on the renin-angiotensin system

Other prior and concomitant medications will be reviewed by a medical panel for potential BP-modifying activity and will be classified accordingly for use in post hoc analyses.

## **6.6. Protocol Deviations**

Major protocol deviations as classified in the CTMS will be summarized across the study period by deviation type using the Enrolled Analysis Set. All protocol deviations will also be listed.

## **7. EFFICACY**

### **7.1. Primary Efficacy Endpoints and Analyses**

The primary endpoint is the change in 24-hour ambulatory SBP from baseline to EOT Visit after switching from high-sodium oxybate to XYWAV for participants with narcolepsy. Only ABPM results denoted as "Valid" or "Valid within Acceptable Limits" may be used for analysis. "Invalid" results may be repeated as per protocol.

#### **7.1.1. Primary Analysis**

An analysis of covariance (ANCOVA) model will be used to estimate the primary efficacy endpoint using the SAS PROC MIXED procedure on the Completer Set. The model will include the change in 24-hour SBP from baseline to EOT Visit as the dependent variable and the mean-centered baseline 24-hour SBP as an independent variable in the model.

$$\text{BASE\_CENTERED} = \text{BASE} - \overline{\text{BASE}}$$

Example SAS Code for the ANCOVA model is shown below:

```
proc mixed data = DSET;  
  class avisitn;  
  where avisitn = [EOT];  
  model chg = base_centered avisitn;  
  lsmeans avisitn;  
run;
```

Least-squares mean change from baseline (LS-mean), standard error (SE), 95% confidence interval, and *p*-value will be reported. Unadjusted values at each visit, including change from baseline, will also be summarized as continuous variables.

